### 7.4 Analysis Plan

## 7.4.1 Primary Outcome Analyses

The primary outcome will be self-reported HIV testing uptake in the past three months. We will examine the hypothesis comparing the superiority of the crowdsourced intervention compared to conventional HIV test uptake campaigns. In our study, since the outcome is binary, generalized linear mixed models (GLMM) and generalized estimating equations (GEE) can be used in our study for the primary outcome analysis. However, since we only have eight clusters, GLMM will be used for primary data analysis in our study; GLMM is preferred in studies with a small number of clusters. The model will include intervention status and time as fixed effects and site and individuals as random effects. The estimated intervention effects will be reported with 95% CIs and p values. Descriptive analysis will be

used to summarize the characteristics and behaviours of the participants at baseline and follow-up surveys.

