## 4 Trial Design

## 4.1 Type of Trial

This study will use an adaptation of the stepped wedge randomized controlled trial (RCT) design (Figure 1). In the stepped wedge RCT, study sites are randomized to begin the intervention at different times so that by the end of the study period all sites have initiated the intervention. A total of eight major metropolitan cities - four from Guangzhou Province (Guangzhou, Jiangmen, Zhuhai, Shenzhen) and four from Shandong Province (Yantai, Jinan, Qingdao, Jining) - will implement the crowdsourced intervention. These cities were chosen based on the following criteria: 1) previous CDC MSM sentinel surveillance site; 2) capacity

for campaign implementation; 3) capacity for intervention implementation at community level. Four cities (Guangzhou, Shenzhen in Guangdong Province, Qingdao, and Jinan in Shandong Province) will implement more intensive in-person events to promote engagement during the intervention development phase. Intervention development and implementation are described in detail in later sections.

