## 4.3 Randomization and Stratification

The eight cities will be randomized to initiate intervention in groups of two at three-month intervals (Figure 1). The order of intervention implementation at four cities within each province (Guangdong and Shandong Provinces) will be randomized using SAS software. One city in Guangdong Province and one city in Shandong Province will then begin intervention simultaneously, i.e. city-level randomization will be stratified by province. While waiting to initiate the intervention, cities will continue conventional campaigns that are part of the routine activities of local CDC and CBOs.

Phase	Pre	p.		Inte	erver	ntior	ı									
Months	1	2	3	4	5	6	7	8	9	10	11	12	13	14	15	16
CDC surveillance survey																
Develop intervention and recruit online cohort in 8 cities																
Guangzhou (GD)				*			*			*			*			*
Yantai (SD)				*			*			*			*			*
Jiangmen (GD)				*			*			*			*			*
Jinan (SD)				*			*			*			*			*
Zhuhai (GD)				*			*			*			*			*
Qingdao (SD)				*			*			*			*			*
Shenzhen (GD)				*			*			*			*			*
Jining (SD)				*			*			*			*			*

Figure 1. Stepped-wedge study design

\*represents online survey at baseline and every 3 months thereafter. Gray shading represents roll-out of the intervention. 8 city clusters; 5 time periods; randomization stratified by 2 provinces (Guangdong, Shandong)

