#### 6.2 Intervention Implementation

Phased implementation will be carried out in the eight cities following the stepped wedge RCT design (Figure 1). Implementation in each city will be locally adapted based on crowd feedback from the contest and the designathon. The intervention will be implemented at the individual level (via WeChat messages and SMS) and at the community level (via community partners including CDC, CBOs, and social media influencers) (Figure 2).

For individual-level implementation, the campaign content (images and/or concepts) will first be shown to the online cohort at the end of the baseline survey, and then repeated once every two weeks for the next three months. Half of the online cohort will receive the campaign content via WeChat message while the other half will receive the campaign content via SMS text message. For community-level implementation, community partners in each city will facilitate the campaign using crowdsourced implementation ideas generated from the designathon.

Figure 2. Schematic diagram of intervention development and implementation.

\*Finalist entries will be selected after an initial screening followed by crowd panel and expert panel judging (Detailed under "Crowdsourcing contest").

\*\*Crowdsourcing contest winners will be selected based on expert panel scores.

\*\*\*Individual-level implementation will be divided based on delivery method into two groups: intervention via WeChat message vs. intervention via SMS text message.

a: Crowd involvement in crowdsourcing contest consists of a nationwide, open call for submission of concepts and/or images related to promoting HIV testing among untested individuals.

b: Crowd involvement in designathon consists of multi-sectoral team members working with guidance from professionals to design an intervention plan.
c: Crowd involvement in community-level implementation entails participation in contests and campaign events held by local CDC and CBOs.

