#### HIV self-testing intervention

SESH implementation team will send out cohort participants an invitation of receiving free HIV testing kit through a confidential message on social media. Our research team had friended the participants on social media (WeChat) which allows private interaction with them. Individuals who would like to receive this test kit will be directed to an online form that allows them to provide an alias (not their real name), an address, and their cell phone number. These three identifiers will be stored separately in Guangzhou in a locked cabinet. Our research assistant will identify the cohort participants by checking whether the mobile phone number is registered in our baseline survey. Men who provide their address will have a test kit mailed to them. The HIV self-testing package will be sent to participants. The HIV self-test kit is organized in partnership with Guangzhou Tongzhi (GZTZ), a local CBO. The test kits will be offered by SESH. The cover of the mail box will be labeled as "gift". The mail boxes will be delivered by a courier service. Individuals will be able to implement and interpret the test wherever they want, but will be encouraged to send a photograph of the test result back to our research team through WeChat, which is convenient with a smartphone and has no cost. Individuals who have questions can also contact the study research office in Guangzhou over phone or through social media. Individuals who have a positive test will be able to contact the study research office for information about linkage to care and counseling.

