## 7 Statistical Considerations

#### 7.1 Primary Outcomes

The primary outcome of this study will be HIV test uptake over the previous three months. This will be assessed by self-report during follow up survey and triangulated with HIV testing surveillance data from the CDC. A difference of 10% in testing rate (assuming a proportion of HIV testing of 35% during the crowdsourced intervention period and 25% during the conventional intervention period) was chosen based on existing levels of HIV testing and what would be feasible and have public health importance in the Chinese context. The CDC measurement of the primary outcome will be the difference between HIV testing comparing the three months immediately prior to the intervention and the three months of the intervention.

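### The single intervention-status term rests on an unstated constant effect, and no analysis by time since start is planned beside it

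*Combined protocol and SAP*

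**What the plan says.** - **Model.** Section 7.4.1: "The model will include intervention status and time as fixed effects", with site and individual as random effects. Section 7.4.2 applies similar analyses to the binary secondary outcomes. The further analyses in Sections 7.4.2 and 7.4.3 are by in-person-event city, engagement, age and delivery channel. None is by time since start.
- **Roll-out.** Section 4.3 starts two cities every three months, and Figure 1 states eight clusters and five periods. Section 4.1 says that "by the end of the study period all sites have initiated the intervention". Section 4.3 adds: "While waiting to initiate the intervention, cities will continue conventional campaigns".
- **Duration of components.** Under Section 6.2 the individual-level content is shown at the end of the baseline survey, "then repeated once every two weeks for the next three months". For the community level, "community partners in each city will facilitate the campaign using crowdsourced implementation ideas generated from the designathon", with no end date. Under the heading HIV self-testing intervention, "SESH implementation team will send out cohort participants an invitation of receiving free HIV testing kit", with no timing.
- **Outcome.** Section 7.1 defines testing over the previous three months: "This will be assessed by self-report during follow up survey". The CDC version is a difference "comparing the three months immediately prior to the intervention and the three months of the intervention".

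**The concern.** Each survey looks back three months, so it captures roughly one quarter of exposure. The first pair of cities contributes up to four exposed quarters and the last pair only one. The protocol itself gives reason to doubt that all exposed quarters are alike: the messages stop after three months, the CDC measure treats the intervention as a three-month episode, and the other components are open-ended.

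One status term has to represent all of these quarters. In a stepped-wedge layout with period effects, it does not do so as a plain average, because later exposed quarters can receive negative weight. A fading effect can then be overstated relative to its average, and a building effect can be estimated below its value in every quarter. With no analysis by time since start, the report would not show which had happened. The plan also does not say which effect over time the primary estimate is meant to represent.

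**Working it through.** **Inputs.** Testing 35% against 25%, CV 0.4, 30% loss and 160 men per city are from Section 7.3. The roll-out is from Section 4.3. The plan's loss adjustment reproduces: 91/0.7 = 130 per city, and 130 x 8 = 1,040. The planned 160 gives 160 x 0.7 = 112 per city.

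Variances are p(1-p)/n = 0.30 x 0.70/112 = 0.001875 for a city-period mean and (0.4 x 0.30)^2 = 0.0144 between cities. Correlation within a man is taken as zero because the documents give no value.

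**Method.** Generalized least squares on city-period means, with period effects, a random city intercept and one status term X. The estimate is a weighted sum of the means. Its weight on exposure quarter k is the sum of the coefficients on all city-periods in that quarter.

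**Hand check, status on from start, five periods.** Between-city variance dominates, so the fixed-city limit is close. There, weights are proportional to X - row mean - column mean + grand mean. Row means by step are 0.8, 0.6, 0.4, 0.2; column means are 0, 0.25, 0.5, 0.75, 1; the grand mean is 0.5. Sums over the four steps:

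- Quarter 1: 0.45 + 0.40 + 0.35 + 0.30 = 1.50
- Quarter 2: 0.20 + 0.15 + 0.10 = 0.45
- Quarter 3: -0.05 - 0.10 = -0.15
- Quarter 4: -0.30

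Dividing by the total of 1.50 gives 1.00, 0.30, -0.10, -0.20. With the actual variances the weights are 0.983, 0.300, -0.092, -0.192.

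**Four follow-ups.** Section 5.1 excludes men tested in the past three months, and Section 7.1 assesses the outcome at follow-up. Baseline may therefore carry no outcome information. Without it the weights are 1.163, 0.300, -0.182, -0.282.

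**Assumed effect curves (percentage points).** The documents give none. The average is over exposed city-periods, of which there are 8, 6, 4 and 2 by quarter (20 in all).

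| Quarters 1-4 | Average | Estimate, five periods | Estimate, four follow-ups |
|---|---|---|---|
| 10, 10, 10, 10 | 10.0 | 10.0 | 10.0 |
| 10, 9, 8, 7 | 9.0 | 10.5 | 10.9 |
| 8, 9, 10, 11 | 9.0 | 7.5 | 7.1 |
| 10, 5, 2.5, 1.25 | 6.1 | 10.9 | 12.3 |
| 10, 0, 0, 0 | 4.0 | 9.8 | 11.6 |
| 2.5, 5, 7.5, 10 | 5.0 | 1.4 | 0.2 |

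Examples with five periods:

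- Third row: 0.983 x 8 + 0.300 x 9 - 0.092 x 10 - 0.192 x 11 = 7.5.
- Fourth-row average: (8 x 10 + 6 x 5 + 4 x 2.5 + 2 x 1.25)/20 = 6.1.
- Last row: the single-term SE is 2.48, so a true average of 5.0 points appears as about half a standard error.

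**Sensitivity.** At CV 0.15, the third row becomes 7.7 (five periods) and 7.5 (four follow-ups), and the halving curve 10.2 and 11.1. At an assumed within-man correlation of 0.5, they are 7.5 and 7.0, and 10.9 and 12.5. A logistic fit to expected proportions for the third row gives an odds ratio of 1.44 (1.41 with four follow-ups), against true quarterly values of 1.48 to 1.69. Treating time as linear leaves the stay-on weights unchanged, because the share of cities that are on rises by 0.25 each period.

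**Alternative coding: on for one quarter only.** Row means are 0.2, column means are 0 then 0.25, and the grand mean is 0.2. Each first-quarter cell gets 0.75 and each later cell -0.25. The sums are 3.00, -0.75, -0.50, -0.25, so the weights are 1.00, -0.25, -0.17, -0.08, which total 0.5. A sustained effect of 10 points is then estimated as 5.0, and a first-quarter-only effect of 10 as 10.0.

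**The case against.** **Coding is not established.** The stay-on weights need status to remain on after the first quarter. Sections 4.1 and 4.3 speak of starting, not continuing, and the Figure 1 shading may settle the matter. This stands as a condition. It does not remove the problem, because the one-quarter coding distorts a sustained effect instead. A reader might infer that the plan leaves status undefined; that cannot be concluded from a figure that is not visible. Nor should Table 2 be used to decide: its 91 per city is not reproduced from the Figure 1 layout (the cited formula gives about 71), so it supports neither coding.

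**The target is imported.** No section names the average since start as the estimand, so a reader who infers that the plan contradicts its own estimand goes too far. What the plan has is an unstated assumption and an unnamed target. Against a first-quarter target with five periods, the distortion for fading effects is small: 9.8 and 10.9 against 10. The average itself also depends on a choice: for a first-quarter-only effect of 10 it is 4.0 over exposed city-periods, but 2.5 if quarters count equally.

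**The test of superiority.** A reader might infer a raised false-positive risk. The weights do not support that: if the effect is zero in every quarter, any weighted sum of it is zero.

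**Only if is too strong without qualification.** A non-constant curve can match its average by coincidence. The statement holds in general, not without exception.

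**The alternative is imprecise.** This stands, and it is why the second model is proposed beside the primary one and not in its place.

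**Conclusion.** The point holds in a limited form, and the plan should be changed. The single term carries an unstated constant-effect assumption that the plan's own description of the components makes doubtful, and no planned analysis would show a departure from it.

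Under stay-on coding and five periods, the estimate misses the average over exposed city-periods by about 1.5 points for the mild curves (7.5 or 10.5 against 9.0) and by 4.8 for the halving curve (10.9 - 6.1). It misses by more if baseline carries no outcome information. The consequence is for the reported effect size, and for power when the effect builds.

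The size rests on the coding, on assumed curves common to all cities, and on a linear approximation to the GLMM. No passage predicts growth, so the steepest growth curve is an illustration only. The negative weights follow from the layout and the coding, not from the curves.

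**What to change.** 1. Reconcile Section 6.2, the HIV self-testing text and Section 7.1 on when each component starts and how long it runs. Tabulate intervention status for every city and survey, or refer to Figure 1 if its shading already shows it.
2. Name the primary estimand: the first-quarter effect, or the average since start with its weighting over quarters.
3. Keep the single-term GLMM as primary and label its result as the effect assuming a constant effect.
4. Pre-specify, as a sensitivity analysis, a model with one term per exposure quarter and the same time and random effects. Report the four quarter effects and their stated average with 95% CIs.

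**Cost.** SAP wording, one table and three more model terms; no new data. The price is precision:

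| SE (points) | Five periods | Four follow-ups |
|---|---|---|
| Single term | 2.5 | 2.7 |
| First quarter | 2.7 | 3.4 |
| Quarter 4 | 6.5 | 9.0 |
| Average since start | 3.3 | 4.7 |

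The second model can reveal large departures from constancy but will often not settle the shape. A 3-df constancy test at 5% has power of about 50% for the halving curve and 25% for the steep growth curve with five periods (35% and 16% with four follow-ups). These use a normal approximation with only eight cities and are probably optimistic. A non-significant constancy test must therefore not be read as evidence of a constant effect.

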## 5 Trial Population and Measures

## 5.1 Eligibility

Eligibility criteria will include: currently living and planning to live in the eight cities for the next 12 months; not living with HIV; no HIV test in the past three months; born biologically male and identify as either male or transgender; had oral or anal sex with men at least once during their lifetime; 16 years and older; willing to provide cell phone number (for follow up and incentive delivery purposes); completed the informed consent document. MSM who meet all other eligibility criteria but received testing in the past three months or living with HIV will be invited to complete a single survey, but not followed over time in the cohort.

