#### 5.3 Measures

Information on socio-demographics, sexual behaviors, and psychosocial conditions will be collected using standardized online survey tools. Socio-demographic characteristics include participants' age, highest level of education completed, annual income, marital status, sexual orientation, and sexual orientation disclosure. Behavioral and psychosocial variables include self-reported HIV testing, syphilis testing, HIV self-testing, HIV test-associated stigma, frequency of sex, condom use (condomless sex, sex always with condom, and no sex), HIV testing social norms, HIV testing self-efficacy, community engagement, campaign engagement, MSM empowerment.

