## 7.3 Sample Size Calculation

We used a binary outcome stepped-wedge randomized controlled trial design for sample size calculation. The required sample size is calculated for the primary outcome. To calculate sample size, we assumed that a crowdsourced intervention will be superior to a conventional method in promoting HIV testing among MSM who never tested for HIV. Assuming a proportion of HIV testing of 35% during the crowdsourced period and 25% during the conventional period, total number of clusters of eight, total number of time period for intervention of four, coefficient of variation of 0.4 (usually between 0.15 and 0.4), 2-sided alpha=0.05, 90% power, and 30% loss to follow up, then the total sample size will be 1040 men (130 for each city). To further improve the power for sub-analysis and secondary outcomes, we will increase the sample size to 1280 men (160 for each city). The calculation was made using the formulas developed by Michael A. Hussey et al. (http://faculty.washington.edu/jphughes/pubs.html).

Table 2	: samp	le size	calculation
---------	--------	---------	-------------

		NT I						Loss	Sample	Total
		Number	Number	Coefficient			Sample	to	size for	sample
Pi*	Pc \$	of	of time	of	Alpha	Power	size/no	follow	aach	size (8
		clusters	periods	variation @			LTFU	10110 W	cacii	5120 (0
			-					up	cluster	clusters)

30	20	8	5	0.4	0.05	0.9	80	30%	114	912
30	20	8	5	0.15	0.05	0.9	71	30%	101	808
30	15	8	5	0.4	0.05	0.9	31	30%	44	352
30	15	8	5	0.15	0.05	0.9	26	30%	37	296
35	25	8	5	0.4	0.05	0.9	91	30%	130	1040
35	25	8	5	0.15	0.05	0.9	83	30%	119	952
35	20	8	5	0.4	0.05	0.9	37	30%	53	424
35	20	8	5	0.15	0.05	0.9	31	30%	44	352
40	30	8	5	0.4	0.05	0.9	99	30%	141	1128
40	30	8	5	0.15	0.05	0.9	93	30%	133	1064
40	25	8	5	0.4	0.05	0.9	42	30%	60	480
40	25	8	5	0.15	0.05	0.9	36	30%	51	408
45	35	8	5	0.4	0.05	0.9	104	30%	149	1192
45	35	8	5	0.15	0.05	0.9	99	30%	141	1128
45	30	8	5	0.4	0.05	0.9	45	30%	64	512
45	30	8	5	0.15	0.05	0.9	40	30%	57	456

Note: \*Pi: probability of HIV testing during intervention period; \$Pc: probability of HIV testing during control period; @ usually between 0.15-0.4.

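### The primary GLMM uses no baseline information on the men, so it has no protection if survey non-response depends jointly on intervention status and testing history

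*Combined protocol and SAP*

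**What the plan says.** The primary outcome is binary: "The primary outcome will be self-reported HIV testing uptake in the past three months" (7.4.1). For the GLMM, the same section states: "The model will include intervention status and time as fixed effects and site and individuals as random effects". No participant covariate is named, and baseline characteristics appear there only in a descriptive summary.

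The cohort is restricted to men with "no HIV test in the past three months" (5.1). Men tested more recently "will be invited to complete a single survey, but not followed over time in the cohort".

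Predictors of testing are nevertheless collected (5.3): "Socio-demographic characteristics include participants' age, highest level of education completed, annual income, marital status, sexual orientation, and sexual orientation disclosure". The same section adds: "Behavioral and psychosocial variables include self-reported HIV testing, syphilis testing, HIV self-testing, HIV test-associated stigma, frequency of sex". Section 7.4.2 has a secondary outcome limited to men with previous HIV testing, so testing history is evidently recorded and expected to vary. Age is used only as a subgroup (7.4.3).

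The sample size (7.3) assumes "2-sided alpha=0.05, 90% power, and 30% loss to follow up". No missing-data method and no covariate-adjusted model for the primary outcome is given.

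**The concern.** In many cohorts the baseline outcome carries much of what is known about each participant's propensity. Here it is constant, so the individual random effect has to learn that propensity from at most four binary follow-up answers, and from fewer once men miss surveys.

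The campaign reaches cohort men on their phones every two weeks for three months (6.2), and cell phone numbers are also taken for follow-up (5.1). It is conceivable that messaging changes who answers the surveys, and does so differently for never-testers and previous testers. The men observed under intervention would then differ in testing propensity from those observed under control. Part of that difference would be read as an intervention effect. If never-testers were the ones to fall silent, the error would favour the superiority hypothesis.

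**Working it through.** **Inputs from the documents.** 35% versus 25% tested, 30% loss, 8 cities, 160 men per city, CV 0.4 with a usual range of 0.15 to 0.4 (7.3); five surveys (Figure 1); about 40% of MSM never tested (3.1), hence 60% ever tested.

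**Assumed, because the documents give no figures.** Testing rates by history, response rates by history and intervention status, and the spread of individual propensity.

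**1. The plan's own loss figure.** 91/(1 − 0.30) = 130 per city; 130 × 8 = 1040. This reproduces. The 91 itself does not: the cited formula gives 71 to 73 per city at the stated inputs. That discrepancy errs towards more men and does not affect this point.

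**2. Baseline outcome.** Every cohort man has the value 0, so it has no variance and cannot serve as a covariate. Four informative follow-ups remain.

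**3. Mechanism, by hand.** Let ever- and never-testers test at pE and pN with no true effect, and respond equally under control but at rE and rN under intervention. The ever-tested share among responders under intervention is s = 0.6·rE/(0.6·rE + 0.4·rN). The crude shift is (s − 0.6)(pE − pN).
- Mild: 30%/17% tested, 80%/65% responding. s = 0.48/0.74 = 0.649; shift = 0.049 × 13 = 0.6 points.
- Strong: 35%/10% tested, 85%/50% responding. s = 0.51/0.71 = 0.718; shift = 0.118 × 25 = 3.0 points.

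The random intercept uses each man's other answers and removes part of this.

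**4. Mixed model, zero true effect.** Large-sample simulation on the probability scale, with man random intercept and city and period terms; response 75–80% under control, and 80–85% (ever) versus 45–65% (never) under intervention.
- Intermittent non-response: unadjusted bias about 0.3 to 2.4 points (2.5 at the most extreme setting, 80% versus 45%); within about 0.3 points after adjustment for testing history.
- Monotone dropout, about 25–30% missing: about 0 to 0.4 points unadjusted.
- Monotone dropout, less favourable settings: 0.3 to 0.9 points if the differential is confined to the first intervention period; 0.6 to 1.3 points at 32–39% missing, falling to within 0.25 after adjustment.

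**5. Logistic GLMM, true OR 1.649.** Paired entries are for a prior-testing OR of 2 and of 4; individual SD 1.

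| Loss pattern | Missing | OR unadjusted | OR adjusted | Log-OR shift |
|---|---|---|---|---|
| None | 0% | 1.629; 1.638 | 1.629; 1.638 | 0.000; 0.000 |
| History only (never 40%, ever 23%) | 30% | 1.637; 1.641 | 1.639; 1.645 | −0.001; −0.002 |
| Intervention only (20% to 40%) | 33% | 1.659; 1.679 | 1.660; 1.680 | 0.000; 0.000 |
| Joint: control 20%, intervention never 50%/ever 25% | 29% | 1.726; 1.794 | 1.660; 1.665 | 0.039; 0.075 |
| Joint: control 20%, intervention never 60%/ever 20% | 30% | 1.764; 1.889 | 1.649; 1.662 | 0.068; 0.128 |
| Joint, monotone: per-survey hazard control 8%, intervention never 20%/ever 5% | 21% | 1.649; 1.650 | 1.645; 1.644 | 0.002; 0.003 |

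At 160 men per city and about 30% missing the standard error is 0.146. The joint intermittent shifts are therefore 0.039/0.146 = 0.27 to 0.128/0.146 = 0.88 standard errors. If shifts of that size also arose under the null, two-sided type I error would be Φ(−1.96 + 0.27) + Φ(−1.96 − 0.27) = 5.8%, up to Φ(−1.96 + 0.88) + Φ(−1.96 − 0.88) = 14.2%, instead of 5%.

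**6. Precision.** With 91 men per city, individual ICC 0.1–0.7 and a covariate explaining 10–50% of between-man variance, the variance of the effect falls by 0.01–0.13% at CV 0.4 and by 0.13–2.3% at CV 0.15. In the logistic model with prior-testing OR 2, the standard error with and without testing history is 0.120 in both cases without loss, and 0.146 in both cases at 30% loss.

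**The case against.** A GLMM with site and individual random effects and no covariates is a legitimate primary analysis for a randomised stepped wedge. A reader might infer that it is valid only if loss is unrelated to testing history. That is not so: loss depending on history alone, or on intervention alone, moved the log OR by 0.002 or less.

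A reader might also infer that precision is being thrown away. Within-city and within-man comparisons carry most of the information, so time-constant covariates add almost nothing. A saving of several percent would require the covariates to explain much of the between-city variance as well, which nothing in the documents supports.

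Nor do the documents support saying that the effect will be biased upward. They give no response rates by testing history, and the direction depends on who stops answering. The plan pays for each follow-up and offers a prize chance for completing all surveys (5.2.1), and it triangulates self-report with CDC surveillance data (7.1). The 30% allowance in 7.3 is called loss to follow-up, which most naturally means dropout, the pattern with the smaller bias. All of this stands, and it limits the size and certainty of the concern.

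It does not remove it. Surveys every three months can be missed intermittently, the payments do not make response equal across groups, and the triangulation does not change the specified model. Adjustment is harmless if the pattern is absent: without loss, both models give the same odds ratio.

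**Conclusion.** The concern holds as a conditional weakness. The primary model uses no information on the men at entry, and the outcome's own baseline value is uninformative by design. If non-response depends jointly on intervention status and testing history, the unadjusted effect can shift by about 0 to 2.4 points of the 10-point target. Intermittent non-response accounts for most of that range. Monotone dropout at about 30% missing contributes little, though heavier dropout, or a differential concentrated in the first intervention period, contributes more. Adjusting for testing history removes nearly all of the material bias.

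These sizes rest on 60% ever tested and on assumed testing rates, response rates and individual heterogeneity. They show what could happen and are not a forecast. The bias results support testing history specifically; age and education are added as collected predictors that cost nothing.

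**What to change.** In 7.4.1, add to the primary model, as fixed effects, baseline HIV-testing history (ever versus never tested, as collected), age and education. State the coding of each before outcome data are analysed, and report the model without them as a check. Give protection against differential non-response as the reason, with no claim of added power.

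Use ever versus never tested. Section 5.3 says only that self-reported HIV testing is collected, so time since last test is not shown to be available. If the cohort proves to contain only never-tested men, as 7.3 assumes but 5.1 does not require, the testing-history term drops out and age and education remain.

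The cost is one sentence in the plan and one extra reported model. No new data are needed, and the standard error is essentially unchanged. Section 9 says analysis is still pending, so the change can still be pre-specified.
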